6.2 Safety and Tolerability Assessments

Safety and tolerability will be assessed by the frequency, severity, and causality of AEs and SAEs, vital sign measurements, laboratory assessments, physical examinations, suicidality assessments, and seizure diary. Safety and tolerability assessments will be conducted according to the schedule presented in Table 6-1.

6.2.1 Adverse Events

6.2.1.1 Definitions of Adverse Events

The investigator is responsible for reporting all AEs that are observed or reported during the study, regardless of their relationship to study drug or severity. Each study participant's LAR/caregiver will be instructed to contact the study center if the study participant experiences any AEs, including whether there was any change in the study drug administration (e.g., dose withheld, dose reduced, or dose missed).

An AE is defined as any untoward medical occurrence in a study participant enrolled into this study regardless of its causal relationship to study drug. Each study participant's LAR/caregiver will be instructed to contact the investigator at any time after enrollment if any new or worsening symptoms develop.

Treatment-emergent AEs (TEAEs) are defined as AEs that start or increase in severity after the first dose of study drug in this open-label study. All AEs occurring after the study participant receives the first dose of study drug must be reported to Ovid or its designee via the eCRF.

Anticipated day-to-day fluctuations of preexisting disease(s), condition(s), or behavior(s) present or detected at the start of the study that do not worsen are not AEs. Lack of drug effect is not an AE. Social and/or convenience situations and/or admissions to the hospital, where an untoward medical occurrence did not occur, are not AEs.

Cases of pregnancy that occur during maternal or paternal exposures to study drug are to be reported. Data on fetal outcome and breastfeeding are collected for regulatory reporting and drug safety evaluation.

Study staff will record the occurrence and nature of each study participant's preexisting conditions (e.g., prior to enrollment in ELARA), including clinically significant signs and symptoms of the disease under treatment in the study (e.g., seizures, motor dysfunction, sleep disruption, anxiety), as part of the medical history.

As seizures are often a baseline condition in study participants with AS, seizures should be reported as an AE in any of the following circumstances:

- There is a clear increase in the frequency of seizures compared to the study participant's baseline.
- There is an emergence of a new seizure type.
- The study participant experiences status epilepticus.
- The investigator believes the seizure should be captured as an AE (in which case the investigator should document their reasoning).

Seizures in this study participant population will be detected and assessed using the seizure diary (Section 6.2.2.4). Diaries will be collected at the study site during the study and will be analyzed by the sponsor along with the reportable SAEs in evaluating risks and benefits.

After the ICF is signed, study staff will record any change in the condition(s) and the occurrence and nature of any AEs. If a study participant experiences an AE after the ICF has been signed but before receiving study drug, the event will be reported and will be included in the study participant's medical history unless the event is serious, or the investigator feels the event may have been caused by a protocol procedure.

6.2.1.2 Serious Adverse Events

An SAE is defined as any event that:

- Results in death
- Is immediately life threatening
- Requires inpatient hospitalization or prolongation of existing hospitalization

- Results in persistent or significant disability/incapacity
- Is a congenital anomaly or birth defect

Important medical events that may not result in death, be life threatening, or require hospitalization may be considered SAEs when, based upon appropriate medical judgment, they may jeopardize the study participant or may require medical or surgical intervention to prevent one of the outcomes listed in this definition. Examples of such medical events include allergic bronchospasm requiring intensive treatment in an emergency room or at home, blood dyscrasias or convulsions that do not result in inpatient hospitalization, or the development of drug dependency or drug abuse.

6.2.1.3 Eliciting and Documenting Adverse Events

Adverse events will be assessed beginning at enrollment (date of signed informed consent) and up to 30 days after the last dose of study drug. Adverse events must be followed until resolution or for 30 days after the study participant's last study drug dose, whichever comes first.

After informed consent is obtained, at every clinic, phone and/or home health visit, study participants and their LAR/caregivers will be asked a standard nonleading question to elicit any medically related changes in their wellbeing. They will also be asked if they have been hospitalized, had any accidents, used any new medications, or changed concomitant medication regimens (both prescription and over the counter medications).

In addition to study participant observations, AEs identified from any study data (e.g., laboratory values, physical examination findings) or identified from the review of other documents (e.g., study participant diaries) that are relevant to study participant safety or considered to be clinically significant, in the medical and scientific judgment of the investigator, will be documented on the AE page in the eCRF.

6.2.1.4 Reporting Adverse Events

All AEs reported or observed during the study will be recorded on the AE page in the eCRF. Information to be collected includes the following:

- Drug treatment
- Dose
- Event term
- Time of onset

- Investigator-specified assessment of severity and relationship to study drug
- Time of resolution of the event
- Seriousness
- Any required treatment or evaluations
- Outcome

Adverse events resulting from concurrent illnesses, reactions to concurrent illnesses, reactions to concurrent medications, or progression of disease states must also be reported. All AEs will be followed to adequate resolution. The Medical Dictionary for Regulatory Activities (MedDRA) will be used to code all AEs.

Any medical condition that is present at the time that the study participant is screened and remains stable should not be reported as an AE. However, if the condition worsens at any time during the study, it should be recorded as an AE. In general, an elective procedure is not considered an AE unless it is required to address worsening of an underlying condition. In this case, the underlying AE should be reported and not the procedure.

Any abnormal laboratory test results (hematology or clinical chemistry) or other safety assessments (e.g., vital sign measurements), including those that worsen from baseline, that are felt to be clinically significant in the medical and scientific judgment of the investigator are to be recorded as AEs.

6.2.1.5 Reporting Serious Adverse Events

All AEs must be recorded in the eCRF upon awareness.

Any AE that meets SAE criteria (Section 6.2.1.2) must immediately (i.e., within 1 business day) inform Ovid Drug Safety upon learning of any SAE that occurs (whether or not attributable to the study drug). It is the investigator's responsibility to ensure that SAE reporting procedures are followed appropriately. All SAE reports and any revisions to an SAE report must be sent to the email address provided below. All supporting source information concerning the SAE (e.g., hospital records) should also be provided by email.

[REDACTED]

If there is a question concerning an SAE, the site needs guidance regarding the reporting of an SAE, the site is returning a call from an Ovid Drug Safety specialist, the site urgently needs to report an SAE or make Ovid Drug Safety aware of an SAE, the safety hotline should be used (country-specific hotline numbers provided in a separate document).

If an SAE is reported via the hotline, the site should first submit the SAE paper form and then enter the SAE in the eCRF. Any AE that meets SAE criteria (Section 6.2.1.2) must be entered into the EDC system immediately (i.e., within 1 business day) after study staff first learn about the event, in addition to emailing the SAE Report form. Once the qualifying SAE data are entered into the EDC system, Ovid will be notified by an email alert that will contain high-level safety information.

All SAEs must be reported starting from the time that informed consent for study participation is provided. If the investigator becomes aware of an SAE within 30 days after the study participant's last dose of study drug or within 30 days after the last study visit, the SAE must be reported. Serious AEs must be followed until the event resolves, the event or sequelae stabilize, or it is unlikely that additional information can be obtained after demonstration of due diligence with follow-up efforts (i.e., the study participant or health care practitioner is unable to provide additional information, or the study participant is lost to follow-up). Serious AEs that occur more than 30 days after the last dose of study drug should be submitted to the sponsor if the investigator becomes aware, however, these do not need to be reported to the IRB/IEC or regulators unless the investigator or sponsor considers them related to study drug.

6.2.1.6 Suspected Unexpected Serious Adverse Reactions and Nonserious Adverse Events of Special Interest

The sponsor will promptly evaluate all suspected unexpected serious adverse reactions and nonserious AEs of special interest against cumulative product experience to identify and expeditiously communicate possible new safety findings to investigators, IRBs and independent ethics committees (IECs), and applicable health authorities based on applicable legislation.

To determine reporting requirements for single AE cases, the sponsor will assess the expectedness of these events using the current OV101 investigator's brochure. (Ovid Therapeutics Inc. 2018).

The sponsor or its legal representative is responsible for notifying the relevant regulatory authorities of SAEs meeting the reporting criteria. This protocol will use the appropriate section of the current investigator's brochure as the Reference Safety Document. The expectedness and reporting criteria of an SAE will be determined by the sponsor from the Reference Safety Document.

6.2.1.7 Assessment of Severity

The severity, or intensity, of an AE refers to the extent to which an AE affects the study participant's daily activities. The intensity of the AE will be rated as mild, moderate, or severe using the following criteria:

- Mild:** An AE that is transient in nature and generally does not interfere with the study participant's normal activities.
- Moderate:** An AE that is sufficiently discomforting to interfere with the study participant's normal activities.
- Severe:** An AE that is incapacitating and prevents normal activities.

Changes in the severity of an AE should be documented to allow an assessment of the duration of the event at each level of intensity to be performed. Adverse events characterized as intermittent do not require documentation of the onset and duration of each episode.

6.2.1.8 Assessment of Causality

The investigator's assessment of an AE's relationship to study drug is part of the documentation process, but it is not a factor in determining what is or is not reported in the study. If there is any doubt as to whether a clinical observation is an AE, the event should be reported.

The relationship or association of the test article in causing or contributing to the AE will be characterized using the following classification and criteria:

- Unrelated:** This relationship suggests that there is no association between the study drug and the reported event.
- Possible:** This relationship suggests that treatment with the study drug caused or contributed to the AE, i.e., the event follows a reasonable temporal sequence from the time of drug administration or follows a known response pattern to the study drug but could also have been produced by other factors.

Probable: This relationship suggests that a reasonable temporal sequence of the event with drug administration exists and, based upon the known pharmacological action of the drug, known or previously reported adverse reactions to the drug or class of drugs, or judgment based on the investigator's clinical experience, the association of the event with the study drug seems likely. The event disappears or decreases on cessation or reduction of the dose of study drug.

Definite: This relationship suggests that a definite causal relationship exists between drug administration and the AE, and other conditions (concurrent illness, progression/expression of disease state, or concurrent medication reaction) do not appear to explain the event. The event reappears or worsens if the study drug is re-administered.

6.2.1.9 Follow-Up of Study participants Reporting Adverse Events

All AEs must be reported in detail on the appropriate page in the eCRF and followed to satisfactory resolution, until the investigator deems the event to be chronic or not clinically significant or until the study participant is considered to be stable.

6.2.2 Other Safety Assessments

Safety assessments other than AEs (Section 6.2.1) include assessment of suicidality, vital sign measurements, laboratory assessments (Section 6.7), physical examinations, and seizure diary.

6.2.2.1 Clinical Assessment of Suicidality

The full ABC-Irritability subscale (ABC-I) will be administered. The ABC-I will be used to assess suicidality instead of the Columbia-Suicide Severity Rating Scale, since cognitive impairment in patients with AS interferes with the understanding of the concept of suicide. Most individuals with AS are not able to communicate thoughts of suicidality, so the study participant's irritability reported by the LAR/caregiver is being used as a surrogate measure of suicidality. The investigator will review the scale items with the LAR/caregiver at each scheduled timepoint. If grading worsens, the investigator must decide whether that indicates a potential for self-harm by the study participant, and if so, must document it as an AE and closely monitor it until resolution. The entire Aberrant Behavior Checklist – Community (ABC-C) will be administered, although only the ABC-I will be used to assess the potential for self-harm.

6.2.2.2 Vital Sign Measurements

Vital sign measurements will include height, weight, blood pressure, heart rate, and temperature. Measurements of blood pressure, heart rate, and temperature should be attempted after the study participant has been resting in a supine or sitting position for at least 10 minutes.

6.2.2.3 Physical Examinations

A physical examination will include a relevant general assessment of: head, eyes, ears, nose and throat; neck; heart; chest (including lungs); abdomen; extremities; skin; lymph nodes; as well as neurological and cardiovascular systems.

6.2.2.4 Seizure Diary

The seizure diary is a caregiver-reported clinical outcome assessment measure that captures the total number and duration of seizures. Caregivers will record the number, duration, and type of seizures each day using the paper seizure diary. Please also see Section 6.2.1.1 for AE reporting criteria for these seizure events.

The caregiver will be trained by the site with specific instructions beginning with the screening visit to ensure compliance in recording seizures. The seizure diary will be completed each day during the study, beginning at Screening (Baseline for study participants entering this study within 2 weeks of completing the EOT visit of OV101-19-001) and continuing through the EOT. Seizure diaries will be collected and reviewed by the investigator with the study participant's caregiver for proper recording at specified timepoints (Table 6-1). Seizure Identification Form and Diagnostic Review Forms (SIF/DRF) will be completed by site personnel for every eligible study participant. This information will be faxed or emailed to The Epilepsy Study Consortium (TESC) for review and approval. The SIF/DRF will be used to ensure that the seizures are classified accurately. SIF and DRF forms will be collected for patients who have enrolled/completed the study if feasible.

For the prospective baseline period, the seizure frequency (expressed as a 28-day frequency) will be calculated as

$$(\text{number of seizures}) / (\text{number of days seizures were assessed}) \times 28$$

Seizure frequency calculated through this method will be used to confirm the eligibility.

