*Telehealth/Virtual visits for dose adjustments may be made throughout the treatment phase at the discretion of the investigator

The following study participants will be required to complete screening and baseline visits (and assessments) to determine eligibility before receiving OV101 under this protocol:

- Study participants who completed OV101-15-001 or OV101-16-001
- Study participants who are siblings of study participants who have completed OV101-15-001, OV101-16-001, or OV101-19-001
- Study participants who completed treatment in OV101-19-001 more than 2 weeks before completing the baseline visit under this protocol (OV101-18-002)

For study participants required to complete the screening and baseline visits, the planned duration of study participation is approximately 166 weeks from the start of screening to the EOS visit, including 160 weeks of treatment with OV101.

For study participants completing the EOT visit for OV101-19-001 two weeks or less before enrolling in this OV101-18-002 protocol, the OV101-19-001 EOT visit may serve as the baseline visit for OV101-18-002. Clinical laboratory results assessed at EOT in OV101-19-001 will serve as baseline clinical laboratory results in OV101-18-002. For such study participants, the maximum planned duration of study participation would be approximately 162 weeks or until commercially available.

Study participants who meet all eligibility criteria will be enrolled on Day 1 (baseline visit) and start the study drug that evening at bedtime (not in the clinic). Each study participant's legally acceptable representative (LAR)/caregiver will receive a package of study drug at the baseline visit, sufficient to last until the Week 12 visit.

As presented in Figure 3-1, each study participant's dose of OV101 will be titrated to a maintenance dose, as tolerated by the study participant [REDACTED]. The maximum tolerated dose (up to 15 mg at bedtime) will be maintained to the EOT. [REDACTED]
[REDACTED]
[REDACTED]

Phone calls to manage titration will occur on Days 6 and 11 for all study participants. [REDACTED]
[REDACTED] Phone calls to manage dose titration, [REDACTED] will occur 5 days later to assess tolerability.

[figure not shown]

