6.1 Study Visits

6.1.1 Screening Period

Study participants entering this study within 2 weeks of completing the EOT visit of OV101-19-001 do not need to have a screening period; the screening activities can be verified or conducted at the baseline (Day 1) visit. All other study participants will be screened for participation in the study up to 30 days before Baseline (Day 1), when the first dose will be administered. Study participants who meet all entry criteria can have their baseline clinic visit at any time during the screening period.

Written informed consent (from the study participant's LAR/caregiver) and assent (from the study participant) will be obtained before the study participant participates in any study procedure and begins the study screening procedures for eligibility. Assent will be obtained if the investigator believes that the study participant has the intellectual capacity to provide it, but assent may not be relevant based on the study participant's intellectual disability and/or age (Section 9.3).

Molecular confirmation of the diagnosis of AS was an inclusion criterion for OV101-15-001, OV101-16-001, and OV101-19-001. Blood tests for molecular confirmation of AS will not be performed unless the study participant is a sibling of a previous participant and does not have prior documented molecular confirmation.

During the screening period, the investigator will determine whether the LAR/caregiver and study participant are able to complete all questionnaires and assessments that require their contributions and will also assess their ability to comply with study procedures.

In preparation for participation in this trial, LAR/caregivers will be educated on the clinical safety data for OV101 obtained thus far and will be trained to report assessments and to identify, manage, and report any potential AEs.

The LAR/caregiver will be provided with a sleep diary for documenting the study participant's sleep and a seizure diary for documenting the study participant's seizures. The LAR/caregiver will record data in the sleep diary for at least 7 days before each clinic visit. A calendar reminder will also be provided for recording data in the sleep diary.

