6.1.2 Baseline Visit

For study participants entering this study within 2 weeks of completing the EOT visit of OV101-19-001, the EOT visit activities need not be repeated at the baseline visit. The EOT visit of OV101-19-001 can serve as the baseline visit for the present study. Screened study participants will return to the study site for the baseline (Day 1) visit, and the LAR/caregiver will bring the study participant's completed sleep and seizure diaries for review by study staff. Study staff will collect the sleep diary (for recording in the eCRF) and will review it for completeness. If quality issues are detected, study staff will again instruct the LAR/caregiver in the proper use of the sleep diary. A new sleep diary will be issued to the LAR/caregiver for use in the 7-day period preceding the Week 2 clinic visit. A calendar reminder will also be provided for the start of sleep diary assessments.

Before dispensing study drug, study site staff must confirm appropriate completion of the sleep and seizure diaries and fulfilment of all eligibility criteria (Section 4.1). Study participants who meet all eligibility criteria will receive study drug at Baseline as described in Section 5.2.

Screening and baseline assessments must be performed within a 30-day period. If the screening and baseline visits are separated by no more than 14 days, the following assessments do not need to be repeated at the baseline visit: medical history, clinical assessment, physical examination, clinical laboratory tests, and determination of concomitant medications.

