- Notify [REDACTED] advance of the visit to define IP shipment arrangements.

- Informed consent/addendum/assent should be sent to the study participant and LAR/caregiver either electronically (pdf format) or by mail prior to the scheduled Baseline visit.
 - Informed consent/addendum/assent can be performed via Telehealth/virtual and/or Telephone during the Baseline Visit and documented in the source document with the date and time of the verbal consent/assent. A home nurse visit will replace a virtual visit if the latter is not feasible.
 - Documentation of the consent/assent must be captured in the study participant's source documents. Please ensure the following is documented:
 - The date and time of the consent/assent.
 - Method of consent/assent (Telehealth/virtual or Telephone).
 - Individuals who signed consent/assent (Site personnel and Participant's LAR/caregiver).
 - Method by which the signed consent/assent will be provided to the Site.

Study Participant can provide proof of wet ink signature via fax, scan or picture. Site should advise Caregiver to bring in the original ICF/assent with wet ink signature at next possible on-site visit or via courier envelope provided by the Site at their earliest convenience.

- For remote screening, ensure that the Study Participant has access to [REDACTED] Baseline Visit clinical labs, vital sign testing, and weight measurement may be performed at a local lab or by the home health nurse.
- Copies of seizure and sleep diary forms should be sent to LAR/caregivers.
 - Electronic copies may be provided if LAR/caregivers can make physical copies.
 - Instructions for completion of diary forms should be provided verbally/in writing to the LAR/caregivers.
 - Pre-paid envelopes should be provided by the site to the LAR/caregivers by the site to support the shipping of the diaries.
- ALL scale administrations should capture the CGI-S-AS/CGI-I-AS, PedsQL, and CSHQ data on the paper source even when administered by phone. Please still use [REDACTED] to score the Vineland-3.
- Update EDC accordingly.

Guidance for Baseline Visits for study participants scheduled beyond 2 Weeks of completing NEPTUNE

- For these study participants a Screening Visit must have been performed prior to Baseline.
- Baseline visits can ONLY occur when study participants can appear ON-SITE.

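### Seizure frequency: Section 6.1.5 conflicts with daily diary recording, direct rollovers from OV101-19-001 have no stated baseline diary window, and percent change fails at a zero baseline

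*Combined protocol and SAP*

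**What the plan says.** **Endpoint and analysis.** The 28-day seizure frequency is a safety endpoint (Section 7.1) under a secondary objective (Section 2.2). Section 7.7.1 and the Synopsis plan the frequency at baseline and afterwards, and the percent change from baseline, for all seizures and for drop and nondrop subtypes. Section 7.7 also plans a separate analysis of seizure diary data in NEPTUNE (OV101-19-001) participants and leaves detailed methods to a separate SAP, which is not part of the text reviewed.

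**Recording.** The Synopsis, Section 3.1 and Section 6.2.2.4 call for a seizure entry every day. Section 6.1.5 says that the new sleep and seizure diaries handed out at clinic visits are for the week before the next clinic visit.

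**Baseline.** Section 6.2.2.4 starts the diary "beginning at Screening (Baseline for study participants entering this study within 2 weeks of completing the EOT visit of OV101-19-001". It computes the rate in a prospective baseline period as seizures divided by days assessed, times 28. No length or minimum number of days is given.

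**Direct rollovers (entry within 2 weeks of the OV101-19-001 EOT visit).** They need no screening period, because "the screening activities can be verified or conducted at the baseline (Day 1) visit" (Section 6.1.1). Section 3.1 says that "the OV101-19-001 EOT visit may serve as the baseline visit for OV101-18-002", and Section 6.1.2 says much the same. The Pandemic Addendum (Section 13) says that data from the last NEPTUNE visit supply the baseline visit. Elsewhere Baseline is the dosing day: participants are "enrolled on Day 1 (baseline visit) and start the study drug that evening at bedtime" (Section 3.1), and screening for everyone else runs "up to 30 days before Baseline (Day 1), when the first dose will be administered" (Section 6.1.1). The default in Section 7.7 is the last non-missing evaluation on or before the first-dose date.

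**Eligibility.** No inclusion criterion requires seizures (Section 4.1.1). Section 4.1.2 excludes only poorly controlled seizures.

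**The concern.** A 28-day rate needs a numerator and a known set of observed days. The recording conflict puts the observed days after Week 12 in doubt. The rollover rule puts the baseline days in doubt for one entry route. Percent change then divides by that baseline, which can be zero.

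The Introduction reports that seizure occurred more often on OV101 than on placebo in the Phase 2 study, so movement from no seizures to some is a pattern that this summary should be able to show. Two of the gaps are also hard to repair later. Diary days that caregivers were never asked to record, and pre-dose days that were never observed in this study, cannot be recovered at the analysis stage.

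**Working it through.** The plan gives no seizure rate and no figure to reproduce, so the check sets the passages side by side and adds simple arithmetic.

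**1. Coverage if Section 6.1.5 is followed literally.** Clinic visit days from Table 6-1: 84, 252, 448, 672, 896, 1120. Section 6.1.5 governs diaries issued from Week 12 on.

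- Intervals: 168, 196, 224, 224 and 224 days, sum 1036 (= 1120 − 84).
- Share per interval: 7/168 = 4.2%, 7/196 = 3.6%, 7/224 = 3.1%.
- Total: 5 × 7 = 35 days; 35/1036 = 3.4%, against 100% under daily recording.

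**2. Pre-dose diary days for direct rollovers.**

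- *Baseline is the first-dose day.* The diary starts that day, so there are 0 pre-dose days, or 1 if Day 1 is counted. The formula gives 0/0 × 28 (undefined) or, with one day and one seizure, 1/1 × 28 = 28 per 28 days. The addendum fits this reading, since "Informed consent/addendum/assent can be performed via Telehealth/virtual and/or Telephone during the Baseline Visit" for these participants, but it applies only once the sponsor has activated it in writing.
- *Baseline is the earlier EOT visit.* If a diary were issued then, up to about 14 pre-dose days could exist. No section says that one is issued.
- *General rules.* The EOT visit, the last NEPTUNE visit and the last non-missing evaluation each identify a visit or an evaluation. None says which diary days form the denominator, or whether OV101-19-001 kept a comparable diary. If it did, its pre-treatment period and its last weeks are different comparators. Section 7.7.2 names the previous study's baseline for durability of improvement; nothing similar is said for seizures.

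**3. Percent change at zero.** Percent change = 100 × (post − base)/base. With base = 0 it is undefined for every post value, including 0. A participant may have a zero baseline in one subtype even when the overall baseline is not zero.

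**Illustration only.** Assume Poisson counts with r seizures per 28 days and D diary days. Then P(zero baseline) = exp(−rD/28).

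| r | D = 1 | D = 14 |
|---|---|---|
| 2 (assumed) | 93.1% | 36.8% |
| 4 (assumed) | 86.7% | 13.5% |
| 12 (ceiling) | 65.1% | 0.2% |

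The value 12 is 3 per week × 4 weeks, the most that the count criterion in Section 4.1.2 admits; it is not an expected rate. The shares of direct rollovers and of seizure-free participants are not given, so the number of participants affected cannot be computed.

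**The case against.** Much can be said for the plan. Three places require daily recording, and only one sentence departs from them. Section 3.1, Section 6.8.1.2 and the sleep-diary footnote to Table 6-1 tie the 7-day window to the sleep diary, so sites would probably record seizures daily. The rollover baseline is not left without any rule, because the addendum names the last NEPTUNE visit and Sections 3.1 and 6.1.2 allow the EOT visit to serve. Rules for zero denominators and minimum diary days are ordinary SAP content. Absolute frequencies, medians and participant listings are already planned.

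This lowers the weight but does not settle the points. The text of Section 6.1.5 still contradicts the other sections. A named visit still does not define a window for a rate. An SAP can handle a zero baseline, but it cannot supply diary days that were not collected.

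Four stronger readings are tempting, and the documents do not support them.

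- *Direct rollovers certainly have no baseline.* The EOT visit may serve as Baseline, so a longer window is possible.
- *New-onset seizures would go unseen.* Absolute frequencies and adverse event reports would show them; only the percent-change summary cannot.
- *Direct rollovers cannot pass the eligibility or dispensing checks.* Section 6.1.2 says that "study site staff must confirm appropriate completion of the sleep and seizure diaries and fulfilment of all eligibility criteria" before drug is dispensed, but it introduces diary return for screened participants. The eligibility sentence in Section 6.2.2.4 follows a statement about the prospective baseline period. Both can be read as not reaching direct rollovers.
- *Seizure adverse event reporting fails for want of a baseline.* Section 6.2.1.1 has staff record pre-enrollment conditions, seizures included, as medical history, and three of its four triggers need no baseline comparison.

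**Conclusion.** The point holds in three limited parts.

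1. Section 6.1.5 contradicts the daily seizure recording required elsewhere. Read literally it leaves 3.4% of days after Week 12 observed, although the sentence was probably meant for the sleep diary.
2. Direct rollovers have no seizure-specific baseline source or window. If Baseline is the first-dose day, they have no pre-dose diary day in this study, or one. If it is the EOT visit, they may have up to about 14.
3. Percent change cannot include zero-baseline participants, who are eligible, so movement from no seizures to some cannot appear in that summary. This part depends on the separate SAP, which may already cover it.

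Severity is minor to moderate. The sample size is not based on power (Section 7.4), the analysis is descriptive, and other planned outputs would show new seizures. The zero-baseline percentages rest on an assumed Poisson model and are not evidence about this population.

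**What to change.** - **Section 6.1.5:** reconcile the seizure-diary sentence with daily recording in the Synopsis and Sections 3.1 and 6.2.2.4.
- **Section 6.2.2.4:** for direct rollovers, state the source and window of the seizure baseline. Use OV101-19-001 diary data if they exist, and say whether the window is that study's pre-treatment period or its last weeks. If there are no such data, summarise on-study rates only.
- **Section 7.7.1 or the SAP, unless the SAP already does this:** add absolute change from baseline and a shift table of seizure-free against not seizure-free that keeps zero-baseline participants. Report percent change only for nonzero baselines, as median and IQR, with the number excluded. If the SAP covers this, a cross-reference is enough.

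The cost is a few sentences, one added table and a little extra analysis. Percent change would be reported for fewer participants, and OV101-19-001 diary data, if they exist, may have to be merged.
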